1.4.1. Minor complications

There are reports of a 3% to 28% prevalence of minor complications ^{23, 24}, with spontaneously resolving hematuria accounting for 13.2% to 18.9% ^{22(,)(23)(,)(25)}; pain occurs in 25% of cases ²² and catheter migration ranges from 12% to 17% ^{10) .. (22)}

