1.5.1. The Biofilm Question

Colonization of the nephrostomy catheter occurs as soon as it is passed into the patient¹⁹, leading to the development of a three-dimensional biofilm²⁸, containing a high concentration of microorganisms which are under relative protection from both the immune system and antimicrobials, associated with intraluminal fouling can lead to catheter dysfunction and clinical infection, from pyelonephritis and abscesses to bacteremia and septic shock^{18, (29)}.

Biofilm is therefore a reservoir of microorganisms which can perpetuate an episode of infection or even facilitate a new one¹⁹. Therefore, the best way to prevent infection is to use the nephrostomy catheter for as short a time as possible. However, if patients need this catheter for a long period of time, one way of mitigating catheter-related urinary tract infection would be to change the catheter after a period of use.

The time used to change the catheter varies according to expert opinion and institutional protocols, ranging from 10 weeks³⁰ to 3 months³. One study proposed a model to define the best time to change, associated with fewer complications, better patient compliance and lower costs, concluding that changes could be made every 60 days⁽²⁰⁾.

In situations where urinary tract infections related to the nephrostomy catheter recur, a retrospective study suggests that the catheter should be changed up to four

(4) days after starting the appropriate antimicrobial to treat the current infection and maintain this antimicrobial for 14 days of treatment ⁽¹⁹⁾.

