4.10.1. Definitions

In order to carry out this study, it is necessary to establish some concepts, some of which are not yet standardized in the medical literature:

- **Urinary tract colonization:** occurs when there is a positive uroculture result (presence of infectious agents such as bacteria or fungi) in the absence of clinical signs suggestive of infection. In these cases, antibiotic treatment is not necessary (45).
- **Urinary tract infection:** occurs when there are signs and symptoms suggestive of local infection, such as cystitis (bladder infection or lower urinary tract infection) or pyelonephritis (kidney infection or upper urinary tract infection) associated with a positive uroculture result, requiring treatment with antibiotics ^{3, 19, (46)}.

- **Urinary tract infection related to the percutaneous nephrostomy procedure:** when the urinary tract infection occurs shortly after the procedure has been carried out, in this case, percutaneous nephrostomy (first pass or catheter changes).
- **Urinary tract infection related to the nephrostomy catheter:** when the urinary tract infection occurs at another time unrelated to the procedure and in the presence of the nephrostomy catheter and in the absence of another focus justifying the infection.

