4.10.4. Urinary tract infection

A urinary tract infection will be considered to be the presence of clinical signs and symptoms suggestive of infection, such as fever (axillary temperature greater than 37.8°C), chills, low back pain, pain at the wrist-percussion of the lumbar region and/or the presence of cloudy urine in the collection bag, plus a uroculture with the presence of microorganisms (no more than two) with more than 100,000 CFU/ml.

If the urinary tract infection is diagnosed 7 (seven) days after the procedure (first catheter passage or change), it will be considered a procedure-related urinary tract infection.

If a urinary tract infection is diagnosed between catheter changes, it will be considered a catheter-related urinary tract infection.

The laboratory tests to be studied will be blood count, creatinine and urea, C-reactive protein, type I urine, uroculture and antibiogram and samples of blood cultures and antibiograms collected at the time of diagnosis of the urinary tract infection.

If the participant receives treatment for a possible urinary tract infection occurred between catheter changes at another service, it will be considered an infection if there is an improvement in the symptoms reported by the participant in the medical records and the antimicrobial used for the treatment will be verified.

The antibiotic(s) used for treatment will be duly studied and registered

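### The UTI rule in Section 4.10.4 lets cloudy urine alone plus a positive culture count as infection, so the primary outcome can include colonisation; its wording also differs from Section 4.10.1

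*Protocol*

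**What the plan says.** Protocol Section 4.10.4 calls an event a UTI when there are signs suggestive of infection. Its examples begin with raised temperature, chills and back pain, and the list ends "pain at the wrist-percussion of the lumbar region and/or the presence of cloudy urine in the collection bag, plus a uroculture". The culture criterion is "plus a uroculture with the presence of microorganisms (no more than two) with more than 100,000 CFU/ml". The list is introduced as examples, it is joined by and/or, and no sign is mandatory. Sections 4.10.2 and 4.10.3 refer to Section 4.10.4 for the 7-day procedure-related outcome and accept any report of signs in the chart.

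Section 4.10.1 gives the general definitions. Colonisation is a positive culture "in the absence of clinical signs suggestive of infection". UTI is signs of local infection "associated with a positive uroculture result, requiring treatment with antibiotics". Section 4.10.4 does not repeat the treatment clause.

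The background states: "Colonization of the nephrostomy catheter occurs as soon as it is passed into the patient" (Section 1.5.1).

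The SAP lists the same signs, adds leukocyturia, leukocytosis and organ dysfunction as variables, and plans neither a stricter outcome nor a sensitivity analysis on the definition.

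**The concern.** The primary objective is the rate of procedure-related UTI by use of prophylaxis. Under Section 4.10.1 only the absence of suggestive signs separates colonisation from infection. Section 4.10.4 lists cloudy urine as such a sign, so cloudy urine alone moves a culture-positive patient from one category to the other. In a population with indwelling catheters, part of the measured rate may then be colonisation.

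The group comparisons are also exposed. Under Section 4.10.3 a catheter change counts as targeted only if a culture taken about 7 days earlier showed a specific agent; otherwise it is studied as empirical. Targeted changes are studied at the Jales hospital, and the Barretos hospital contributes empirical changes. Prior bacteriuria therefore differs between the groups by construction. Local habits in charting cloudy urine or sending cultures could differ as well.

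**Working it through.** **1. The two definitions applied to one case.** Take a patient within 7 days of a procedure who has cloudy urine, no fever, chills or pain, one organism above 100,000 CFU/ml, and no antibiotic judged necessary.
- Section 4.10.4: one listed sign plus the culture, so UTI.
- Section 4.10.1, UTI: not met, because the treatment clause fails.
- Section 4.10.1, colonisation: not met either if cloudy urine is a suggestive sign, as Section 4.10.4 says it is.

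The same patient is a UTI under one section and belongs to neither category under the other.

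**2. Comparison with the definitions reviewed in Section 1.4.3.** These rest on fever or abnormal temperature, chills, flank or percussion pain, hypotension or entry-site cellulitis, in various combinations with laboratory findings. None lists cloudy urine. The nearest is pyuria, which one definition accepts only together with fever and flank pain. Pain is different: one cited definition, from a cancer cohort, accepts flank or percussion pain alone with at least 10^5 CFU/ml and no more than two species.

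**3. Possible size.** Section 4.9 gives 372 first passes and 358 changes (372 + 358 = 730). The plan states no power or misclassification figure. Section 1.5.2.3 cites a cancer cohort with 7.5% asymptomatic bacteriuria and 19% pyelonephritis after first passage (90-day follow-up), and 2% and 4% after changes. It also cites the institution's earlier 7-day UTI rates of 1.2% and 11.4%. Section 1.4.1 says "pain occurs in 25% of cases". No frequency of cloudy urine is given, so the share of bacteriuric patients showing an unrelated sign is assumed: 25% for pain (independent of bacteriuria), 100% for cloudy urine as a ceiling.

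| Route | Non-infections counted | Infections, by rate used | Ratio |
|---|---|---|---|
| First pass, pain | 372 × 0.075 × 0.25 = 7.0 | 372 × 0.19 = 70.7 | 10% |
| First pass, pain | 7.0 | 372 × 0.012 = 4.5 | 156% |
| Changes, cloudy urine in all | 358 × 0.02 = 7.2 | 358 × 0.04 = 14.3 | 50% |
| Changes, cloudy urine in all | 7.2 | 358 × 0.114 = 40.8 | 18% |

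The 1.2% and 11.4% rows set bacteriuria from a cohort followed for longer against 7-day infection in another cohort. No row estimates the 7-day false-positive rate.

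**4. Possible effect on the comparison at changes.** Let f be the chance that a patient without infection is counted. Then observed rate = true + (1 − true) × f. All values of f here are assumed, as is a 1:1 split (179 per group), with a two-sided 5% test.
- Equal f = 5%, true rates 14.8% empirical and 6.4% targeted (the earlier cohort): 0.148 + 0.852 × 0.05 = 19.1% and 0.064 + 0.936 × 0.05 = 11.1%. The odds ratio moves from 0.39 to 0.53, and power falls from about 73% to 56%.
- Unequal f, 10% empirical and 2% targeted, no true effect at 11.4%: 0.114 + 0.886 × 0.10 = 20.3% and 0.114 + 0.886 × 0.02 = 13.2%. The risk ratio is 0.65, with about a 44% chance of a significant result. Exchanging the two values of f reverses the direction.

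**The case against.** Four points on the other side have weight.

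- **Catheter colonisation is not a qualifying culture.** Section 1.5.1 speaks of the catheter. The rule needs more than 100,000 CFU/ml in urine and at most two organisms, and the cited bacteriuria rates of 7.5% and 2% are far from universal. The signs must also be suggestive of infection. This stands: colonisation can be counted, but nothing shows how often it would be.
- **The pain criterion has precedent.** A reader might infer that puncture pain is being counted as infection. The documents do not support that: pain without a qualifying culture never counts, and one pain sign plus culture matches a definition the protocol cites. The 25% pain figure comes from a mixed series of mainly stone cases. What remains is that the wording "in the absence of another focus justifying the infection" is attached only to catheter-related UTI, so low back pain alone is a lesser concern.
- **The two sections may be meant to be read together.** Sections 4.10.2 to 4.10.4 record where UTI was treated and with which antibiotic, so treatment may be assumed rather than deliberately dropped. That is plausible, but the operative rule does not say it.
- **Direction.** A reader might infer that antibiotics suppress bacteriuria and so create a spurious benefit of prophylaxis. The documents do not establish this, and selection of the targeted group on a positive culture could pull the other way.

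**Conclusion.** The concern holds as a defect of outcome definition. Cloudy urine alone with a qualifying culture can be counted as UTI, no definition reviewed in the protocol supports that sign, and Sections 4.10.1 and 4.10.4 must be reconciled.

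Its size cannot be fixed from the documents. A reader could take from the table that false events outnumber true ones at first pass, or that they add half again at changes. The first pairs 90-day bacteriuria with a 7-day rate from another cohort; against the 19% of the same cohort the addition is about 10%. The second takes the lower of two available infection rates and assumes cloudy urine in every bacteriuric patient; against 11.4% the addition is about 18%. The power and bias figures show only what the assumed values of f would do.

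The direction of any bias is likewise open. It could differ between targeted and empirical changes, because the groups differ by prior culture result and largely by hospital. The correction is worth making because the remedy is cheap and shows whether the result depends on the definition.

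**What to change.** This concerns how events are classified for analysis, not how patients are treated.

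1. Use one UTI wording in Sections 4.10.1 and 4.10.4, and state whether need for treatment is part of it.
2. Do not let cloudy urine alone plus a positive culture qualify; class it as colonisation.
3. Report results under the stricter definition (at least one of fever, chills where charted, or lumbar or percussion pain, plus the culture criterion) and under the present broad one.
4. Add a sensitivity analysis limited to events treated with antibiotics for UTI. Treatment should not be the sole gate for the main outcome: it depends on clinicians' decisions, prophylaxis type largely follows hospital, and the SAP itself allows that leukocyturia, leukocytosis or a positive culture may have driven the decision to treat.

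Cost: mainly a recode. Fever, low back pain, percussion pain, cloudy urine and treatment antibiotics are listed in Section 4.10.5 and in the SAP's study variables. Chills are not listed there and may need chart lookup. The stricter definition will have fewer events and so less precision. The SAP is written in the past tense; if the data have already been extracted, the stricter version should be labelled a sensitivity analysis rather than replace the primary definition.

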3.2. Secondary

- Describe the frequency of urinary tract infection related to the percutaneous nephrostomy catheter that occurs between catheter changes (not related to the procedure, but possibly to colonization of the catheter);
- To describe and compare the results of the urocultures involved in the study, as well as their sensitivity to the antibiotics used;
- Describe the main signs and symptoms involved in urinary tract infection related to the procedure and the nephrostomy catheter;

- Assess the severity of urinary tract infections according to the type of treatment and the need for hospitalization.
- To determine the risk factors for urinary tract infection related to the passage and subsequent changes of nephrostomy catheters.
- Describe the rates of urinary infections and associated germs according to the time of nephrostomy passage, first passage or catheter change.
- Report whether these catheters were changed when the urinary tract infection occurred and on which day after the urinary tract infection was diagnosed.

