4.7. Exclusion criteria

- Use of percutaneous nephrostomy for other procedures such as passage of a double-J catheter via the antegrade route.
- Use of percutaneous nephrostomy to treat clinical conditions other than malignant ureteral obstruction, such as stenosis secondary to Bricker's ileal conduit.
- Use of percutaneous nephrostomy to clear the urinary tract of non-neoplastic causes, such as stones or non-malignant stenosis.
- Use of antibiotics to treat urinary tract infection when performing percutaneous nephrostomy (first pass or exchange).
- Patients on suppressive antibiotic therapy.

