4.9. Sample size calculation

The retrospective cohort will be made up of 372 consecutive, non-probabilistic patients for convenience, according to data collected from the institution's hospital

system (SisOnco). These patients will be studied according to the procedures performed, divided into first catheter passage and catheter change.

In the first pass of the percutaneous nephrostomy catheter group, 372 procedures were carried out at the Barretos and Jales Cancer Hospitals. In the catheter change group, 358 procedures were carried out in the stipulated period. Totaling 730 procedures carried out at the two hospitals between January 2013 and June 2020.

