4.10.5. Study variables

The study variables will make up the research instrument used to collect the data (see Appendix II).

Sociodemographic and clinical variables: gender, color, age, weight, height, underlying neoplastic disease, performance status and number of organs affected by metastases. Presence of fever, low back pain, pain at the wrist-percussion of the lumbar region, pain in the hypogastrium, dysuria and polyuria and presence of cloudy urine.

Radiological data: degree of urinary tract obstruction.

Dates of diagnosis of the underlying neoplasm and diagnosis of malignant ureteral obstruction.

Laboratory data: blood count, creatinine, urea, type I urine, uroculture and antibiogram.

Antibiotics: for the prophylaxis or treatment of urinary tract infection and sensitivity of the first antibiotic used for prophylaxis and/or treatment.

Colonizing and infecting agents and their classification in terms of multidrug-resistant organisms

Period of use of the catheter(s); removal of the catheter(s); other complications, such as mobility of the catheter(s) and/or obstructions.

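### Catheter-related infection has two definitions and no stated at-risk period or denominator, so the planned frequency cannot be read as a risk or a rate

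*Protocol*

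**What the plan says.** The first secondary objective (Protocol 3.2) is to "Describe the frequency of urinary tract infection related to the percutaneous nephrostomy catheter that occurs between catheter changes". The operational rule in 4.10.4 matches it: "If a urinary tract infection is diagnosed between catheter changes, it will be considered a catheter-related urinary tract infection". The same section applies this restriction again to infections treated at another service.

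The conceptual definition in 4.10.1 is wider. An infection is catheter-related "when the urinary tract infection occurs at another time unrelated to the procedure and in the presence of the nephrostomy catheter", provided that no other focus explains it. No later change is required.

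Section 4.10.3 puts elective changes about 90 days apart, counted from the first pass or the previous change. It allows earlier changes for obstruction, migration or a catheter-related infection. Section 4.7 excludes "Use of antibiotics to treat urinary tract infection when performing percutaneous nephrostomy (first pass or exchange".

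The analysis sections (Protocol 4.12 and the SAP) plan frequency tables, chi-square or Fisher tests and logistic regression, with procedures treated as independent. Neither document gives a denominator for this objective, a rule for when a catheter period ends, or any analysis that uses follow-up time. Yet "Period of use of the catheter(s); removal of the catheter(s" are among the study variables in 4.10.5, and the SAP lists the same items.

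**The concern.** Two analysts following different sections would count different infections. One would require a change at the end of the catheter period; the other would count everything after the procedure window while a catheter was in place. Periods that end in removal or death, or that are still open when data collection stops, fall under the second rule but not clearly under the first. Section 1.3 describes permanent palliative use and section 5 confirms that some participants have died, so such periods will occur.

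The measure raises a second difficulty. A percentage of periods gives a 30-day and a 90-day period equal weight, although section 1.5.1 calls the shortest possible catheter use the best prevention. Section 3.2 also asks for infection rates by first passage or change. Beyond the 7-day window, that contrast mixes infection risk with time in place.

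Section 4.7 adds an ambiguity. If an exchange done under treatment for infection is excluded, it is unclear whether the infected period before it stays in the data. The last objective in 3.2, whether and when catheters were changed after an infection, needs exactly those exchanges.

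**Working it through.** **Inputs from the documents.** 372 first passes, 358 changes and 730 procedures (4.9); planned interval about 90 days, with earlier changes possible (4.10.3); 7-day procedure window (4.10.2, 4.10.3).

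**Assumptions, for illustration only.** One catheter period per procedure; constant infection rate after day 7; risk of 10% or 20% by day 90; periods without a closing change lasting 30 to 120 days. The documents give none of these figures.

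**Step 1: periods without a closing change.** 372 + 358 = 730, which reproduces the stated total. Each change closes at most one period, so at least 730 − 358 = 372 periods have no recorded closing change: 372/730 = 51.0%. At most 358/730 = 49.0% do.

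**Step 2: dwell time alone.** With 10% risk by day 90, the rate is −ln(0.90)/(90 − 7) = 0.1054/83 = 0.00127 per day, or 1.27 per 1,000 catheter-days. The risk over a period of T days is 1 − exp(−0.00127 × (T − 7)): 10.0% for T = 90 and 4.7% for T = 45. The rate is the same, but the percentage is less than half.

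**Step 3: which periods are counted.** If all 358 closed periods last 90 days, they give 358 × 0.10 = 35.8 infections, a frequency of 10.0%. Adding the 372 other periods gives:

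| Length of unclosed periods | Infections in them | Frequency over all 730 | Share of infections in unclosed periods |
|---|---|---|---|
| 30 days | 10.7 | 6.4% | 23% |
| 45 days | 17.5 | 7.3% | 33% |
| 60 days | 24.2 | 8.2% | 40% |
| 90 days | 37.2 | 10.0% | 51% |
| 120 days | 49.7 | 11.7% | 58% |

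If infections in unclosed periods were dropped but 730 kept as denominator, the result would be 35.8/730 = 4.9%. With 20% risk by day 90, the change-closed frequency is 20.0%, against 12.9% to 23.2% over all periods. The rate per 1,000 catheter-days is constant throughout, at 1.27 (10% risk) or 2.69 (20% risk).

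**Step 4: infection that triggers the change.** A simulation of 2,000,000 periods used the 10% risk and a constant hazard of death or removal of ln(2)/90 per day, so that half of periods would end that way by day 90.

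| Infections prompting an immediate change | Frequency, change-closed periods | Frequency, all periods | Rate per 1,000 days, change-closed | Rate per 1,000 days, all |
|---|---|---|---|---|
| None | 10.0% | 7.1% | 1.27 | 1.27 |
| Half | 11.8% | 7.0% | 1.52 | 1.27 |
| All | 13.5% | 7.0% | 1.76 | 1.27 |

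Catheter-days alone therefore do not solve the problem. Every period must also be included.

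**The case against.** The strongest reply is that nothing is expressly excluded. The objective describes infection "that occurs between catheter changes (not related to the procedure, but possibly to colonization of the catheter", which can be read as shorthand for infection that is not procedure-related. Section 4.10.1 would include last periods, and the variables cover catheter use and removal with no restriction to catheters later changed. This stands: leaving out last periods is one literal reading, and the fault is two definitions that need reconciling.

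It is also fair that the objective is descriptive and secondary. A count of infections between changes answers it as worded, so a reader who infers that the plan gives a wrong answer goes further than the text allows.

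A reader might also infer that the frequency describes mainly patients who stayed infection-free to a scheduled change. The documents do not support that. Changes prompted by infection (4.10.3) would enrich change-closed periods with infections, while the section 4.7 exclusion might deplete them. Nor does 4.7 say that the preceding period is lost.

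A stricter reading that drops every period begun by a first pass is likewise unsupported, because 4.10.3 counts the interval from the first pass as well.

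Finally, a single rate assumes a roughly constant hazard, and several cited studies report proportions over fixed follow-up. This is a reason to add the rate to the count, and possibly a cumulative incidence, rather than to replace the count.

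**Conclusion.** The point holds as a gap in definition and measure. Sections 3.2 and 4.10.4 conflict with 4.10.1, and the literal narrow reading leaves at least 372 of 730 periods (51%) without clear cover. That figure assumes one period per procedure. It counts periods, not infections lost, and it includes those open at the cut-off. The procedure counts do not show bilateral catheters separately.

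The planned frequency cannot be read as a risk or rate, and infections beyond day 7 after first pass and after changes are not comparable when dwell time differs. Under the illustrative 10% risk, the change-closed frequency of 10.0% compares with 6.4% to 11.7% over all periods, and the two agree when unclosed periods also last 90 days. Neither the size nor the direction of the distortion can be settled from the documents. The primary 7-day outcome is not affected. This is an inexpensive improvement worth making.

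**What to change.** 1. Use one definition in 3.2, 4.10.1 and 4.10.4. For every catheter, including the last, start the at-risk period at the end of the 7-day procedure window. End it at the first of change, removal, death, last contact or data cut-off.
2. Beside the count, report events per 1,000 catheter-days, separately after first pass and after changes. Optionally add cumulative incidence with death and removal as competing events, which gives a proportion over a stated time and does not need a constant hazard.
3. State that the antibiotic-treatment exclusion in 4.7 removes the procedure from the prophylaxis comparison only. The preceding catheter period, its infection and the exchange date stay in the data for the secondary objectives.

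**Cost.** This needs wording changes in the protocol and SAP, plus some date abstraction. Period of use and removal are already collected. Dates of death and last contact are not listed variables and would have to come from the records already under review. A single rate rests on a roughly constant hazard, and the report should say so. Patient management does not change.
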